 - b. Hypothesis 2: Measures of high harm avoidance, attentional bias towards negatively valenced stimuli, avoidance behavior in a approach/avoidance task, propensity to display a negative facial expression (e.g., sadness, fear), increased heart rate and skin conductance while viewing negative stimuli, and amygdala activation during a fear conditioning task will load together on a latent construct ("Negative Valence System").
 - c. Hypothesis 3: Latent variable scores of individuals with anxiety or depression will span a two-dimensional space according to these two latent constructs and will show significant variability across DSM IV (or DSM-5) diagnostic categories.
- (2) To obtain a confirmatory sample of n=100 subjects at both sites using the same measurement approaches to determine the reproducibility and robustness of the latent constructs obtained from the exploratory sample.**
 - a. Hypothesis 1: Latent constructs of positive and negative valence systems show good reproducibility in a confirmatory factor analysis.
 - b. Hypothesis 2: Variable reduction can be used to obtain reliable projection onto the latent constructs using latent variable analyses.
 - c. Hypothesis 3: Individuals with clinically severe and impairing anxiety or depression will fall into heterogeneous clusters of dysfunctions within the positive and negative valence systems.
- (3) To obtain a reliability sample of n=50 individuals at UCSD and UCLA that will be re-tested within a month to determine the reliability of the latent constructs.**
 - a. Hypothesis 1: Latent constructs of positive and negative valence systems have good test-retest reliability.
 - b. Hypothesis 2: Latent constructs of positive and negative valence systems have better test-retest reliability than measures from individual units of analyses.

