fMRI Data Analysis. Image analysis pathway: The basic structural and functional image processing will be done with the Analysis of Functional Neuroimages (AFNI) software package¹¹². A multivariate regressor approach detailed below will be used to relate changes in EPI intensity to differences in task characteristics. EPI images will be co-registered using a 3D-coregistration algorithm that has been developed to minimize the amount of image translation and rotation relative to all other images. Six motion parameters will be obtained across the time series for each subject. Based on the distribution of these average motion parameters, subjects will be excluded if the average in any one of these parameters exceeds 2 standard deviations from the mean or if movement exceeds the size of the voxel (4 mm). This assures that differences between groups are not due to differences in movements during scanning. Motion parameters will be used as regressors to adjust EPI intensity changes due to motion artifacts. This has been shown to increase power in detecting task-related activation. All slices of the EPI scans will be temporally aligned following registration to ensure different relationships with the regressors are not due to the acquisition of different slices at different times during the repetition interval.

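### The motion exclusion rule screens on average head position against a sample-derived limit, so it can keep people who move continually, drop people who shifted once, and does not fix one limit for both waves and the retest

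*Combined protocol and SAP*

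**What the plan says.** Under fMRI Data Analysis (image analysis pathway), "Six motion parameters will be obtained across the time series for each subject". The exclusion rule, introduced with the words "Based on the distribution of these average motion parameters", then has two limbs. The first is relative: "subjects will be excluded if the average in any one of these parameters exceeds 2 standard deviations from the mean". The second is fixed: "or if movement exceeds the size of the voxel (4 mm". The plan concludes: "This assures that differences between groups are not due to differences in movements during scanning".

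The plan does not say:

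- whether the average is of signed or absolute values;
- which volume is the base (registration is described only as designed to "minimize the amount of image translation and rotation relative to all other images");
- which subjects form the distribution (one wave, both waves, one site, one task run or the retest session);
- whether a limit set in wave 1 is carried forward.

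No volume-to-volume displacement measure appears anywhere.

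Other layers of motion handling exist. Cross-site imaging consistency describes a quarantine and quality-control pipeline that looks at movement, and a per-volume dispersion covariate. At first level, "Motion parameters will be used as regressors to adjust EPI intensity changes due to motion artifacts". Second level analyses adds realignment parameters as covariates of no interest. Specific Aim 2 calls for a second sample "using the same measurement approaches to determine the reproducibility and robustness of the latent constructs".

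**The concern.** Realignment parameters ordinarily describe head position relative to a base image. Averaging them over a run gives a mean offset. Oscillation about the base cancels out, while a single early displacement persists in the average. A rule built on that average can therefore keep the runs with most movement and discard runs that are nearly still.

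The 2 SD limit is also set by whoever was scanned rather than by what degrades the data. The text allows it to be recalculated in each sample.

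Striatal, orbitofrontal, amygdala and insula signals are indicators in the factor model of the General Statistical Approach. Retained motion adds error to those indicators. If it also tracked symptom severity, it could contribute to a loading. Needless exclusions cost subjects from waves of 100. A limit that changes between samples would mean that Aims 2 and 3 compare samples screened by different standards.

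**Working it through.** The plan states no figure to reproduce here, so the check applies its rule to constructed cases.

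**Inputs from the documents.** TR is 2 s and the reward run is 13 min (fMRI Image Acquisition), so 780/2 = 390 volumes. The limits are 2 SD on any of six averages, and 4 mm. Waves are n=100 and the retest is n=50. **Assumed:** the two motion traces, each in one translation parameter, and the SD of run averages, which the documents do not give (0.2 to 0.7 mm tried).

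**1. Continual mover.** Position is 1.5·sin(2πt/20) mm, sampled every 2 s for the whole run.
- Signed run average: 0.00 mm.
- Largest displacement from base: 1.43 mm, or about 2.9 mm from peak to peak.
- Mean absolute volume-to-volume change: 0.57 mm.

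An average at zero passes the 2 SD limb when the sample mean is near zero, whatever the SD. The 4 mm limb is also passed. The person is kept.

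**2. One shift, then still.** Position is 0 for the first 98 volumes and 1.5 mm for the remaining 292.
- Run average with the first volume as base: 1.5 × 292/390 = 1.12 mm.
- Mean absolute volume-to-volume change: 1.5/389 = 0.004 mm.
- Excluded if 2·SD < 1.12, that is SD < 0.56 mm. At assumed SDs of 0.2, 0.3 and 0.5 mm the person is excluded; at 0.7 mm the person is kept.
- With the base at the end of the run the average is 1.12 − 1.5 = −0.38 mm, and exclusion needs an SD below about 0.19 mm.

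**3. If absolute values are averaged.** With a first-volume base the continual mover scores 0.92 mm and the still person 1.12 mm. The still person still ranks worse, although the mover no longer scores zero.

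**4. How many breach 2 SD.** For a normal variable P(|z| > 2) = 0.0455. For six independent parameters, 1 − (1 − 0.0455)^6 = 0.244. Counting only the upper side, 1 − (1 − 0.02275)^6 = 0.129. Correlated parameters give fewer. The percentage does not depend on how still the sample is, because the SD shrinks with it.

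**5. If the limit is recalculated by sample.** For normal data the standard error of mean + 2 SD is about SD·√(1/n + 4/(2n)) = SD·√(3/n): 0.17 SD at n=100 and 0.24 SD at n=50. Two waves from the same population could differ by ±1.96·√(6/100) = ±0.48 SD (95% range). In simulation the larger of two wave limits was typically 1.09 times the smaller for normal data (95th percentile 1.28), and about 1.14 times for heavy-tailed data (95th percentile 1.45 to 1.54).

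**6. Share of high movers caught.** Simulations of 100 people with drift plus jitter compared the rule with the worst tenth by volume-to-volume motion. Capture ran from roughly 20% to 80%, depending on the assumed drift and jitter scales and on their correlation across people. At the low end this is about the overall exclusion rate of 20%; at the high end it is well above it.

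**7. The fixed limit.** The acquired voxel is 200/64 = 3.125 mm in-plane with 3.1 mm slices, which does not match the 4 mm given as its size.

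**The case against.** The strongest reply is that the rule is one layer of several. Scans are quarantined until they pass quality control that includes movement. The dispersion covariate works volume by volume. Motion regressors enter the first-level model, and movement parameters enter again at second level. The fixed 4 mm limit is the same in every sample. All of this stands, and it reduces artefact in the retained runs. But the quality-control step gives no numeric motion threshold, and the covariates do not change who this rule excludes. The second-level movement covariates are not restated for the factor model, and if they are run averages they are also near zero for the continual mover.

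A second reply is that signed averaging and the base volume are inferred. That is correct. If the sponsor meant average volume-to-volume change, the first two examples fall away, but the text does not say so and the sample-derived limit would remain.

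Four stronger readings are tempting and not supported:

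- **That limits will differ by wave.** The text permits this but does not state it; a pooled distribution fits equally well.
- **That the rule must always remove someone.** It need not: 100 evenly spaced values reach only |z| = 1.71.
- **That the rule does no better than chance.** That result depends on particular assumed scales and on unrelated drift and jitter.
- **That motion tracks anxiety and creates a false negative-valence loading.** Nothing in the documents shows such a link. It is a risk only, and bias in a condition contrast would also need motion that differs between conditions.

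**Conclusion.** The point holds for the exclusion rule itself. On its plain reading, the rule measures offset, can rank a continual mover below a nearly still person, and does not deliver the assurance attached to it. It also leaves open which sample sets the limit, so identical motion could be treated differently in wave 1, wave 2 and the retest.

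The size is uncertain. The 24% breach rate assumes six independent normal parameters. The exclusion of the single-shift case needs an SD of run averages below about 0.56 mm with a first-volume base. The share of high movers caught cannot be narrowed beyond roughly 20% to 80% without real motion data. No effect on the Aim 2 or Aim 3 results has been calculated. Because the other motion controls reduce the harm and the remedy is cheap, this is a change that should be made rather than a flaw that invalidates the plan.

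**What to change.** 1. Replace the averaged-parameter 2 SD criterion with mean absolute volume-to-volume displacement from the six parameters already obtained, stating how rotations are put on a mm scale.
2. State one absolute numeric cut-off before wave 1 is analysed, and apply it unchanged to both waves, both sites and the retest. The documents give no basis for a particular value, so the sponsor must set and justify it.
3. Reconcile the 4 mm limit with the acquired voxel dimensions, and define what displacement it refers to.
4. Use each person's mean displacement as the movement covariate in the second-level analyses, and carry it to the neural indicators in the factor model.
5. Remove or soften the sentence that says movement differences are ruled out.

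The cost is a few lines of processing code and no new data. The small downside is that the number excluded is no longer tied to the sample and may be higher or lower than under the 2 SD rule.

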Specific Aims

The diagnostic system that is currently used for mental disorders is based on verbal report, observable behavior, and clinical phenomena that have been aggregated based on statistical approaches to provide reliable categories¹. However, the connection between psychiatric disorders and their underlying neurobiology has been difficult to establish. The NIMH Research Domain Criteria (RDoC) framework is a heuristic approach to integrate neuroscience with psychopathology². Thus, RDoC is the attempt to develop constructs that (a) connect across units of analysis, (b) are applicable across established diagnostic criteria, and (c) are a point of departure to provide measurable constructs to gain a deeper understanding of psychiatric conditions³.

We focus on the positive and negative valence system domains proposed by the RDoC^{4,5}, using self-report, behavior, physiology, and neural circuit unit of analysis measures, apply them to a clinical population of individuals with anxiety or depression recruited from primary care clinics across two sites and apply latent variable analysis to derive latent constructs of positive and negative valence systems functioning that cut across units of analyses. Our preliminary studies provide initial evidence for the relative independence of measures designed to assess each domain. Building on these studies we will adopt a three stage approach: first, principal component analyses will be used for variable reduction within a task; second, confirmatory factor analyses will be used to determine whether the model of positive and negative valence systems fit with the measures obtained from multiple units of analyses; and third, latent variable analysis will be used to relate measures across different units of analysis. The specific aims of the proposal are:

- (1) To recruit, assess, and analyze self-report, behavioral, physiological, and neural circuit unit of analysis data in an exploratory sample of n=100 treatment seeking anxious and/or depressed individuals presenting to primary care clinics at UCSD and UCLA.**
 - a. Hypothesis 1: Measures of reward sensitivity, attentional bias towards positive valenced stimuli, approach behavior in an approach/avoidance task, propensity to display a happy facial expression, increased respiratory sinus arrhythmia (vagal tone), and activation in the ventral striatum during a reward processing task will load together on a latent construct ("Positive Valence System").

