General Statistical Approach: The goal of this proposal is to derive latent variables that adequately quantify the positive and negative valence domain across different units of analyses. The analysis of the variables that are extracted from each unit (as shown in Figure below) will consist of three steps. First, a principal component analysis will be conducted for each unit of analysis to determine the number of independent degrees of freedom contributing to the variance observed in each unit. For example, we will utilize all facial action units, which have been recorded during viewing of IAPS pictures in a principal components analysis. We expect to extract at least two independent components (as shown in the pilot data sections above). The action units that show the highest correlation with the components will be used for subsequent analyses. Second, we will conduct a confirmatory factor analysis with the variables from each unit of analysis that showed the highest correlation with the principal components and propose two factors – positive valence system and negative valence system. We will subsequently test the statistical significance of the coefficients contributing to the factors. Finally, we will conduct a latent variable analysis as detailed below to relate one unit directly to another unit of analysis.

Unit of Analysis	Measure	Positive System Domain	Negative System Domain
Neural/Circuits	Reward paradigm: BOLD % signal difference during reward or loss trials in anatomically constrained ROIs for (1) Anticipation & (2) Outcome phase	Reward trials - anticipation & outcome phase: Ventral striatum, dorsal striatum (caudate), OFC, amygdala	Loss trials - anticipation & outcome phase: Ventral striatum, dorsal striatum (caudate), OFC, amygdala
	Fear conditioning task: BOLD % signal difference in anatomically constrained ROIs for Conditioning trials (CS+E + CS+U vs. CS-)	n/a	Amygdala, insula
Physiology	HR, SCR, EMG, & RSA while viewing emotional images (IAPs)	RSA/vagal tone - resting state; viewing positive images	HR, SCR, EMG - viewing negative images
Behavior: Facial Expressions	Automatic Facial Action Coding System while viewing emotional images (IAPs)	Positive facial expressions (e.g., AUs 12, 6)	Negative facial expressions (e.g., AUs 4, 15, 1+4, 23, 24)

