proposed factors even given a high common variance a sample size of 50 subjects should suffice. Alternatively, one can take a multiple regression approach to approximate the variance that needs to be accounted for by a given variable. For example, given a sample size of $n=100$, and 10 explanatory variables in the CFA, the minimum detectable $r^2 = 0.156$ with an alpha of 0.05 and a beta of $1-0.8^{120}$. In other words, our approach will be successful if the measurement captures at least 15% of the variance observed in the population. Our prior single regressor analyses revealed correlation coefficients of 0.4 and above, which translates to explaining at least 16% and is therefore consistent with our proposed sample size. Moreover, according to Westland¹¹⁸, several considerations should be given when examining sample sizes for structural equation models. Among these is the notion that latent variables impose an a-priori belief system and re-attribute the variance found among the measures across different levels of analyses. Given our sample size of $n=100$, we will be able to examine a ratio of indicators to latent variables of > 3 . In other words, we will be able to examine at least three latent constructs at one time.

Linear latent variable approach: There is no uniformly agreed upon definition of latent variable analysis¹²¹. However, one approach is to define a latent variable as a variable for which there is no sample realization for at least some observations in a given sample. In this context, the positive or negative valence domain can be considered a latent variable. More formally, the latent variable model consists of a measurement part describing the responses $Y_i = (Y_{i1}, \dots, Y_{ip})'$:

$$Y_{ij} = \nu_j + \sum_{k=1}^l \lambda_{jk} \eta_{ik} + \sum_{r=1}^q \kappa_{jr} X_{ir} + \sum_{k=1}^l \delta_{jk} V_{ijk} \eta_{ik} + \epsilon_{ij},$$

and a structural part describing the latent variables $\eta_i = (\eta_{i1}, \dots, \eta_{il})'$: where $i = 1, \dots, n$ is the index of the sampling unit (e.g. individuals), $j = 1, \dots, p$ is the index of the observed variables (measurements or within cluster observations) and $s = 1, \dots, l$ is the index of the l distinct latent variables. Fundamentally, latent variable approaches can be divided into posteriori latent variables, which are latent variables derived from the

[figure not shown]

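### The plan's only power figure is for an omnibus regression F test, not for the factor-loading tests it plans, so the 15% success condition is not established

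*Combined protocol and SAP*

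**What the plan says.** Power and sample size considerations offers three arguments for the sample size. Only one carries a power figure, and it is introduced this way: "Alternatively, one can take a multiple regression approach to approximate the variance that needs to be accounted for by a given variable". Its inputs are "given a sample size of $n=100$, and 10 explanatory variables in the CFA", alpha 0.05 and power 0.8, giving a minimum detectable r² of 0.156. The plan restates this as a success condition: "In other words, our approach will be successful if the measurement captures at least 15% of the variance observed in the population". It adds that earlier single-regressor correlations of at least 0.4 (16% of variance) fit the chosen sample size. The other two arguments (50 subjects being enough for 10 variables and two factors, and the ratio of indicators to latent variables) state no power.

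The analysis is set out under General Statistical Approach: principal components within each unit of analysis, then a CFA with a positive and a negative valence factor, and then "We will subsequently test the statistical significance of the coefficients contributing to the factors". In Specific Aims, Aim 1 Hypothesis 1 lists six measures ending with "activation in the ventral striatum during a reward processing task will load together on a latent construct". Hypothesis 2 makes the same claim for seven measures, counting heart rate and skin conductance separately. Aim 2 Hypothesis 1 asks for good reproducibility in a CFA, again with n=100.

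**The concern.** The regression F test and the CFA loading tests answer different questions. The F test can reject because one of ten predictors is related to the outcome. The hypotheses say that a whole named set of measures shares a factor. An 80% chance of the first is not an 80% chance of the second, yet the plan moves from one to the other and treats the sample size as settled.

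The measures and their derived factors are the stated deliverable. A reader who takes the 15% condition at face value could over-interpret a non-significant loading in a wave of 100. A measure that does belong might be judged not to, or a true structure might appear not to replicate in the second wave.

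**Working it through.** **Inputs from the plan.** n=100; 10 variables; alpha 0.05; power 0.80; r²=0.156; prior r of 0.4 or more (Power and sample size considerations). Two factors with coefficient tests (General Statistical Approach). Sets of six and seven measures (Aim 1, Hypotheses 1 and 2).

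**Step 1: reproduce 0.156.** For the overall F test, f² = R²/(1−R²) = 0.156/0.844 = 0.185, on 10 and 89 degrees of freedom (critical value 1.94).
- Fixed regressors, noncentrality n·f² = 18.5: power 0.814; detectable R² at 80% is 0.152.
- Random regressors, noncentrality f²·W with W chi-square on 99 df, averaged over W: power 0.800; detectable R² is 0.1559.

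The printed figure is the random-regressor omnibus test.

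**Step 2: is it a per-variable threshold?** For one correlation, r = √0.156 = 0.395. With Fisher's transformation, 0.418 × √97 = 4.11, and power is Φ(4.11 − 1.96) ≈ 98%. So 0.156 is not the detectable value for a single variable, although the text introduces it that way.

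**Step 3: power of the planned test.** Assumptions added here, because the plan does not give them: each measure has communality 0.156 (loading 0.395); 100 complete cases; normal data; a correctly specified two-factor maximum-likelihood CFA; Wald tests at two-sided 0.05; factor correlation 0 to 0.38. Indicators are either 5+5 (the plan's ten, split evenly) or 6+7 (the measures listed in Aim 1). Simulated results:

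| Rule | 5+5 | 6+7 |
|---|---|---|
| One given loading | 75–78% | 83–84% |
| Every loading of one factor | 34–37% | 36–40% |
| Every loading of both factors | 12–14% | 14–17% |

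Across both layouts, allowing one miss on a factor gives about 67–73%, and one-sided tests of every loading of a factor give about 47–57%.

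Other checks at communality 0.156, for every loading of one factor:
- likelihood-ratio tests, 31–36%;
- Wald tests with one loading fixed as marker, 16–21%;
- 90 analysable cases (motion exclusions are planned under fMRI Data Analysis), 25–30%;
- factor correlation −0.3, 37–41%;
- 80% is reached at roughly n=180–200.

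**Step 4: what n=100 can support.** At communality 0.22, every loading of one factor is significant in 77–79% (5+5) or 83–85% (6+7) of samples. At 0.24, both factors reach 76% (5+5) or 83% (6+7); at 0.25, 5+5 gives 81%.

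**Step 5: the prior r of 0.4.** There are two readings.
- Correlation of a measure with its factor: communality 0.4² = 0.16, and power for a full set is about 37–43%.
- Correlation between two equally loading indicators: r = loading × loading, so communality is 0.40, and power for a full set is close to 100%.

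**The case against.** A reader might infer that each Aim 1 hypothesis simply has 34–40% power. The documents do not support that. They never define loading jointly as every coefficient being significant, and no passage says a hypothesis fails on one non-significant loading. The communality reading is also a mapping, drawn from the plan's own restatement of 15.6%, and not a stated CFA input. For one given loading the stated 80% is about right.

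Aim 1 is labelled exploratory, and the Linear latent variable approach section assigns a-posteriori models to that wave, with a-priori models for the confirmatory wave. The Significance section expects the mapping to be complex and partly unknown. The plan also calls the regression an approximation and says no theory-based sample size exists for factor analysis.

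These points stand, and they make the set-level figures conditional. They do not remove the mismatch. General Statistical Approach does not confine the CFA to the second wave, and Aim 2 requires a CFA at n=100. At communality 0.156, no set-level rule examined reaches 80%, including the lenient ones. The lack of a closed formula does not prevent a simulation.

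A second tempting inference is that the r=0.4 argument is disproved. It is not: the plan does not say which variables were correlated, 0.4 is given as a floor, and Step 5 shows that the answer turns on this.

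**Conclusion.** The point holds as a mismatch between the power calculation and the planned test. It is not an arithmetic error, since 0.156 reproduces. The figure does not establish that the approach succeeds when measures capture 15% of variance.

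On the Step 3 assumptions, n=100 is about adequate for one named loading. It falls short for a set: modestly if one miss is tolerated, and substantially if every loading must be significant. The result depends strongly on communality, and the shortfall for one factor closes at about 0.22. The figures apply most directly to the confirmatory CFA and to any CFA run on the first wave.

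No passage says a measure will be dropped for a non-significant loading, so the harm is a risk of misreading and not a planned step. The text should be corrected; enrolment need not change.

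**What to change.** Keep n=100 and amend Power and sample size considerations as follows.

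1. Label 0.156 as the detectable R² of an omnibus regression on 10 variables, used as an approximation.
2. Replace the 15% success sentence with the sensitivity of the CFA and its assumptions. For example: *With 100 complete cases and two factors of five to seven equally loading indicators, two-sided Wald tests have about 75–84% power for a given loading when a measure shares 15–16% of its variance with its factor. About 80% power for every loading of one factor requires about 22%, and for both factors about 24–25%.*
3. State which variables gave the prior correlations of 0.4, and qualify the claim of consistency accordingly.
4. Say what result will count as the measures loading jointly, and in which wave that is tested.
5. State that one non-significant loading in a wave of 100 is not by itself evidence that a measure lies outside the construct.

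The cost is wording and a short simulation. The stated sensitivity becomes less favourable.
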